Bringing Exposure Therapy to Real Life Context with Augmented Reality and Telepsychiatry

Study Protocol

NCT03649347

Document Date: September 22, 2020

Software

The software was developed in collaboration with the AR industry and connects the clinician's computer to the AR headset via Local Access Network (LAN). It provides the clinician with a 3D visual of the surfaces surrounding the participant, obtained from the AR device mapping of the environment. The clinician can use the keyboard to adjust their view of the map 360° to have a better view of any surface. A simple drop-down menu allows the clinician to choose a hologram and a sub-type of the feared object (wolf, jumping, black widow); furthermore, the feared object's color (brown, white, yellow), size, direction of motion, and speed of motion are all clinician-directed manipulations offered. Five unique spider webs are available to place on and between surfaces. At any time, the program can be paused with a single click such that all objects disappear for as long as the clinician sees fit.

The software outputs the number of spiders in the environment, the number of spiders in the participant's field of view, the largest spider, and the distance to the closest spider at any moment. Participant's subjective units of distress (see measures below) can be directly entered into the software during the session. A short video demonstrating the software can be seen here: https://drive.google.com/file/d/1qrHNVjLIVOM8NIguuCtMFnc2fr9IjIkY/view

Device

Microsoft ® HoloLens, a holographic AR device, was utilized. This device was selected for its accurate spatial mapping, a preferred feature for realistic positioning of virtual object on real surfaces. This device is wireless, and operates through LAN connections, granting participants the ability to move and interact freely with the environment and the augmented objects.

Participants

Participants were designated to single session ARET or no treatment control based on the order of enrollment (block designation ABAB; parallel trial design). Inclusion criteria included: 1) current untreated arachnophobia, 2) adults of any sex between the ages of 18 and 45, and 3) willing and able to give written informed consent. Exclusion criteria included: 1) current or previous diagnosis of a psychotic disorder, 2) presence of a substance use disorder within the past six months, 3) current use of psychotropic medications, 4) history of seizure, head trauma, or neurological disease, or 5) an uncorrected visual impairment. All participants provided written informed consent and all study procedures were approved by the Wayne State University Institutional Review Board (IRB# 107517B3F). All research activities occurred at an office clinic at Wayne State University in urban Detroit.

We initially aimed to recruit n=15 individuals per group as part of NCT03649347 Bringing Exposure Therapy to Real-Life Context with Augmented Reality (ARET). This clinical trial is to test the feasibility and efficacy of a novel augmented reality software for the treatment of spider and snake phobias. The sample size of 15 per group, 30 total was chosen for arachnophobia as a pilot feasibility and efficacy trial of the software. This sample size was chosen based on samples found in previous studies for pilot feasibility and efficacy testing of VR and AR platforms (14-20). A priori power analyses were not conducted, however post hoc power analyses were conducted and are reported in the results section. Recruitment and study sessions ran within the year 2019.

Procedure

Treatment group

Prior to the treatment, principles of exposure therapy, using the AR device, and process of the treatment were explained. Participants were told they would be informed of each new level of exposure and would not be surprised or tricked without prompt. They were informed that towards the end of the treatment, if they agreed (which all did), placement and motion of the objects would not be prompted.

For potentiating contextualization of safety learning, exposure therapy took place in two different looking clinic offices. Initially participants were in a bright, windowed office, sitting on a chair in one corner. A small, augmented wolf spider was placed on the floor at the point most distant from the participant. Then a small, augmented jumping spider was presented, followed by a small black widow. At each stage, when the participant reached SUDs of below 4, they would advance to the next level with a larger augmented spider, or to the types of augmented spiders or colors (yellow, brown, white) the participant found scarier. Then augmented spiders were moved horizontally, then slowly toward the participant. Gradually the number, speed of motion, proximity to the participant, and the size of the augmented spiders increased; augmented spiders were also placed, or crawled on the walls or the ceiling, or on a clinical assistant present in the room. Participants were encouraged to walk towards the augmented spiders, sit next to them, and do the same while the augmented spiders were moving. When participants could hold their hand very close to a moving spider with SUDs below 4, this stage was concluded.

Next the participants moved to a darker, windowless office. The same process was repeated. At this stage, participants were also encouraged to walk through an augmented spider web placed on an open doorway, with augmented spiders on it. Ultimately, the participant would be walking around the room, surrounded by tens of augmented spiders crawling around without prompt.

At SUDs below 4, the clinician left the room, and communicated with the participant via telecom. This was to allow the participants to feel comfortable with the feared objects on their own, assuring sense of control and autonomy. This stage usually took less than ten minutes until participants found it comfortable to walk around the room and touch the moving augmented spiders of various size. Treatment ended when the SUDs were below 4.

After the post-treatment BAT, participants were reminded of the principles of exposure therapy and advised to practice at home.

Control group

After filling out the questionnaires, the participants did the BAT. They returned one week, and then one month later for repeating the questionnaires and the BAT.

**Document Date: September 22, 2020** 

All statistical analyses will be performed in SPSS version 25 and R version 3.5.2. Data will be evaluated using standard data screening procedures. A priori power analyses were not conducted as this was a pilot study of a novel software platform; sample size was selected based on previous similar studies. Age, sex, and baseline FSQ, SPQ, and BAT will be compared between groups, in order ensure that groups do not differ at baseline. A two-way repeated measures ANOVAs will be used to measure changes in FSQ, SPQ, BAT, and CEQ over time between and within groups. The grouping variable is whether or not the individual received treatment with single-session augmented exposure. The three timepoints are baseline, one-week follow-up, and one-month follow-up. Box's M will be used to evaluate homogeneity of covariance, Levene's test will be used to evaluate homogeneity of variance, and Mauchly's Test of Sphericity will be used to evaluate sphericity. Wilk's Lambda will be the standard reported test statistic, however when any of the assumptions are violated, Pillai's Trace will be reported. For violations of sphericity, a Greenhouse-Geiser correction will be selected.

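### The planned repeated-measures ANOVA uses, for each outcome, only participants with all three visits, so any missed visit discards observed data that a mixed model would keep

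*SAP*

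**What the plan says.** The SAP's single block of analysis text sets the method: "A two-way repeated measures ANOVAs will be used to measure changes in FSQ, SPQ, BAT, and CEQ over time between and within groups". It fixes the repeated factor: "The three timepoints are baseline, one-week follow-up, and one-month follow-up". It chooses multivariate test statistics: "Wilk's Lambda will be the standard reported test statistic, however when any of the assumptions are violated, Pillai's Trace will be reported". Greenhouse-Geisser is the correction if sphericity fails.

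The only text that comes near missing values is this: "Data will be evaluated using standard data screening procedures". It names no method. The text available for review states no rule for missed visits, no imputation, no analysis population and no expected attrition.

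On size, the Protocol's Participants section says: "The sample size of 15 per group, 30 total was chosen for arachnophobia as a pilot feasibility and efficacy trial of the software". On visits, its Control group section says: "They returned one week, and then one month later for repeating the questionnaires and the BAT". For the treated group, the two follow-up visits come from the SAP's list of timepoints.

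**The concern.** Wilks' Lambda and Pillai's Trace are computed from each person's full set of repeated values. Unless values are imputed first, a person with a gap at any visit leaves that outcome's analysis altogether, and the values already collected from that person go unused. The SAP does not write this down as a rule. It is how the chosen method behaves when run as described.

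Two things are at stake. The first is precision: in a trial of about 30 people, each deleted participant matters. The second is possible bias: if missing the one-month visit is related to how someone fared at one week, those left at one week are a selected group, even though the one-week values of the others were observed.

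**Working it through.** **Inputs from the documents.** 15 per group, 30 in total (Protocol, Participants); three visits and the method (SAP). 15 × 2 = 30 agrees. No other stated figure can be reproduced, because the sample size was taken from earlier studies and not calculated.

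**Assumed inputs.** Chance m of missing each follow-up, independently: 5%, 10% or 20%. Equal correlation ρ between visits: 0.5 to 0.7. Outcome SD 1 and two-sided alpha 0.05.

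**Step 1: who remains.** Expected complete cases = 30 × (1 − m)²:
- m = 5%: 30 × 0.9025 = 27.1
- m = 10%: 30 × 0.81 = 24.3
- m = 20%: 30 × 0.64 = 19.2

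At m = 10%, 30 + 2 × 27 = 84.0 of 90 planned values per outcome are observed. The ANOVA uses 3 × 24.3 = 72.9, so about 11.1 are discarded.

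Some loss is likely even at low rates. If each person has a 5% or 10% chance of missing at least one visit, the chance that at least one of 30 is deleted is 1 − 0.95³⁰ = 78.5% or 1 − 0.90³⁰ = 95.8%.

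**Step 2: variance of the one-week change.** For complete cases, the variance per assigned person is 2(1 − ρ)/(1 − m)². For all available data, add up the inverse covariance matrices of the four visit patterns (both follow-ups, one week only, one month only, neither), weighted by (1 − m)², m(1 − m), m(1 − m) and m². Invert the sum and take the variance of one week minus baseline. At ρ = 0.6:

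| m | Complete cases | All available | Ratio |
|---|---|---|---|
| 5% | 0.886 | 0.829 | 1.07 |
| 10% | 0.988 | 0.862 | 1.15 |
| 20% | 1.250 | 0.942 | 1.33 |

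Across ρ from 0.5 to 0.7 the ratios are 1.07, 1.14 to 1.15, and 1.32 to 1.33.

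**Step 3: power.** Take a 0.9 SD difference in one-week change, with ρ = 0.6 and m = 10%. The SD of change is √(2 × 0.4) = 0.894. The noncentrality is (0.9/0.894) × √(n/2), with n per arm and 2n − 2 df:
- Nothing missing, n = 15: noncentrality 2.76, power 75.8%
- All available data, effective n = 12.15 × 1.146 = 13.9: noncentrality 2.65, power about 72%
- Complete cases, n = 15 × 0.81 = 12.15: noncentrality 2.48, power 66.0%

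The choice of method therefore costs about 6 points (72% against 66%). The other 4 or so (76% against 72%) come from the missing data themselves, and no model recovers them.

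**Step 4: bias at one week.** In a large-sample simulation with ρ = 0.6, the log-odds of missing one month rise by 0.5 to 1.0 per SD of worse one-week score.
- Rule in the treated arm only, with 21–24% of that arm missing: the complete-case one-week effect is overstated by about 0.04–0.08 SD.
- Same rule in both arms, with a 0.9 SD effect: it is understated by about 0.01–0.05 SD. Controls score worse, so more of them are deleted, and those who remain look more improved than controls really are.

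With 15 per arm the standard error of the change contrast is √(2 × 0.8/15) = 0.33 SD, so even 0.08 SD is about a quarter of one standard error.

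**The case against.** **No loss is documented.** Neither document reports a missed visit, and the Protocol describes controls returning at both times. With full follow-up the ANOVA loses nothing and is not biased by missing data. This stands, and it makes every figure above conditional. It does not supply a plan for a visit that is missed.

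**The direction of bias.** A reader might infer that poor responders in the treated arm stay away, so that the plan inflates the treatment effect. The documents do not support that. Untreated controls also have to repeat the BAT, and avoidance is at least as plausible for them. Step 4 shows the sign reversing when both arms follow the same rule.

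**The size of the power loss.** A reader might also set 76% against 66% and charge all 10 points to the ANOVA. That compares no missing data with complete cases. The like-for-like loss is about 6 points.

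**The mixed model is not a cure.** It is valid under missing at random. In simulations with equal correlations of 0.5 or 0.7 and 10–30% missing according to the unseen one-month score, it overstated the one-month change by 6–24%, against 4–16% for complete cases. With correlations 0.5/0.5/0.8 and missingness following the one-month change, the order reversed: 5–13% against 12–33%. Nor is the complete-case result always biased. In the equal-correlation runs, missingness that depended on the one-week score left the one-month change unbiased. These points stand and call for a sensitivity analysis.

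**Scope.** Deletion works outcome by outcome: a missing BAT need not remove the same person's FSQ or SPQ.

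**Timing.** The documents are dated September 2020, the Protocol places study sessions in 2019, and it refers to post hoc power results. A new main analysis may therefore come after the data were seen. That bears on how the change is labelled; it does not remove the weakness.

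**Conclusion.** The point holds as a conditional loss of information. Run as written, the planned ANOVA is a complete-case analysis for each outcome, and nothing in the available text offsets this. Under assumed missed-visit rates of 5% to 20% per follow-up, the one-week contrast has about 7% to 33% more variance than an analysis of all observed values. The power cost of the method is about 6 points at 10% missed, for a 0.9 SD effect and correlation 0.6.

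Bias is possible if attendance at one month depends on the one-week result, but it is modest in the cases examined and of unknown sign. The mechanism is certain. The magnitudes are not, because the documents give no attrition rate, correlation or effect size. This is a correctable weakness and not evidence that any result is wrong.

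**What to change.** Make the main analysis of each outcome a linear mixed model fitted by REML to the one-week and one-month values:
- Fixed effects: group, visit, group-by-visit and the baseline value of the outcome.
- Unstructured within-person covariance, with Kenward-Roger or Satterthwaite degrees of freedom.
- Every assigned participant with at least one follow-up value, in the assigned group.
- The group difference at each visit with its 95% CI.

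Keep the stated ANOVA as a sensitivity analysis. State that the mixed model is valid under missing at random, and add a simple missing-not-at-random sensitivity analysis if any visit is missed. Report how many values are missing by arm, visit and outcome. If the ANOVA has already been run, label the mixed model as added after data collection and report both.

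The cost is revised SAP wording and slightly more analysis work; the SAP already names suitable software ("All statistical analyses will be performed in SPSS version 25 and R version 3.5.2"). With about 30 people the small-sample degrees-of-freedom correction is needed. One gain is that the main analysis no longer switches test statistic on the Box, Levene and Mauchly results.

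### Baseline is analysed as a repeated outcome and not adjusted for, so the group-by-time test is valid but generally less precise than the collected data allow

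*SAP*

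**What the plan says.** The SAP's statistical paragraph sets the model: "A two-way repeated measures ANOVAs will be used to measure changes in FSQ, SPQ, BAT, and CEQ over time between and within groups". The between factor is treatment or no treatment, and for the within factor: "The three timepoints are baseline, one-week follow-up, and one-month follow-up". Wilks' lambda is the default statistic, with Pillai's trace if assumptions fail and a Greenhouse-Geisser correction for non-sphericity.

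Baseline values have one other use: "Age, sex, and baseline FSQ, SPQ, and BAT will be compared between groups". Neither document mentions a covariate. The SAP does not say which ANOVA term (group, time or group by time) is the arm comparison.

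On size, the Protocol (Participants) states: "The sample size of 15 per group, 30 total was chosen for arachnophobia as a pilot feasibility and efficacy trial of the software". Allocation is alternating, ABAB by enrollment order. The SAP adds: "A priori power analyses were not conducted as this was a pilot study of a novel software platform".

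**The concern.** When baseline is a level of the time factor and each arm has its own free baseline mean, the group-by-time effect is built from the arm differences in one week minus baseline and one month minus baseline. Each contrast subtracts the whole baseline score, so it fixes the weight on baseline at 1. The most precise weight is the regression slope of follow-up on baseline, which equals the correlation times the ratio of follow-up SD to baseline SD. Wherever that slope differs from 1, the change score carries avoidable noise.

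Efficacy is a stated aim, the arms are small, and the sample size has no power calculation behind it. A wider interval than necessary makes a real effect easier to miss, and the baseline scores that would narrow it are already collected.

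**Working it through.** **Inputs from the documents.** 15 per arm; three visits including baseline; no covariate. There is no power figure to reproduce; 2 × 15 = 30 agrees with the stated total. For orientation, a follow-up-only comparison with 80% power and two-sided 5% detects (1.960 + 0.842) × √(2/15) = 1.02 SD.

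**Assumed, because the documents give none.** Two-sided 5%; no dropout; the same correlation r between every pair of visits; SD 1 at every visit (varied below); effect d = 0.8 SD at both follow-ups (varied below).

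**Planned group-by-time test.** The two change scores have covariance (1−r)[[2, 1], [1, 2]]. The noncentrality is λ = n d² / (3(1−r)) = 15 × 0.64 / (3(1−r)) = 3.2/(1−r), tested on F(2, 27).

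**Same 2-df joint test with baseline as covariate.** Given baseline, the two follow-ups have variance 1−r² and covariance r−r². Then λ = n d² / ((1−r)(1+2r)) = 9.6 / ((1−r)(1+2r)), reduced by about 26/27 for estimating the slope, tested on F(2, 26).

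| r | λ planned | Power planned | λ adjusted (before 26/27) | Power adjusted |
|---|---|---|---|---|
| 0.3 | 4.57 | 0.42 | 8.57 | 0.68 |
| 0.5 | 6.40 | 0.56 | 9.60 | 0.73 |
| 0.7 | 10.67 | 0.80 | 13.33 | 0.87 |

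Both sides test two degrees of freedom, so the gain does not come from switching to a 1-df test. The ratio of the two λ values is 3/(1+2r), that is 1.88, 1.50 and 1.25. If the univariate F test is used in place of Wilks and sphericity holds, planned power is 0.45, 0.59 and 0.82, so the comparison barely changes.

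**One visit alone.** In units of 2·SD²/n, the variance of the arm difference is 2(1−r) for change from baseline and 1−r² for ANCOVA. The ratio is 2/(1+r) = 1.54, 1.33 and 1.18. Power at one month is 0.43, 0.56 and 0.78 for change, against 0.58, 0.67 and 0.83 for ANCOVA. To match ANCOVA with 15 per arm, a change-score test needs 15 × 2/(1+r) = 23.1, 20.0 and 17.6 per arm.

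**Level.** Simulated rejection rates under no effect were 0.046 to 0.055 for all methods.

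**Where the gain fades.** These are the same 2-df tests, with one assumption changed at a time:

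| Change | Planned (r = 0.3 / 0.5 / 0.7) | Adjusted |
|---|---|---|
| Follow-up SD 1.25 × baseline SD | 0.53 / 0.67 / 0.87 | 0.68 / 0.73 / 0.87 |
| Follow-up SD 1.5 × baseline SD | 0.60 / 0.72 / 0.88 | 0.68 / 0.73 / 0.87 |
| Effect 1.5 SD | 0.93 / 0.99 / 1.00 | above 0.99 throughout |

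In the SD rows the effect is 0.8 of the follow-up SD. At a ratio of 1.5 the slopes are 1.5r = 0.45, 0.75 and 1.05, close to the weight of 1 that a change score imposes, and the one-visit variance ratio falls to 1.15, 1.04 and 1.00. At r = 0.9 with equal SDs and d = 0.8, both tests have power of about 1.00.

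**The case against.** The planned test is valid, and the loss depends on values the documents do not give. The Protocol admits only people with current untreated arachnophobia, so a narrower spread at baseline than at follow-up is plausible, and that shrinks the loss. The comparator is no treatment, so the effect may be large enough for either test to find it. All of this stands, and it limits the claim's size. A large effect removes the power gap, although the interval from the change score remains wider whenever the slope is not 1.

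Allocation is the second objection. Participants alternate by enrollment order and the Protocol does not describe randomization. Baseline adjustment presumes equal expected baselines. If the arms differed systematically, change scores and ANCOVA could target different quantities, and change scores would remove a stable gap that ANCOVA removes only in part. So the planned analysis does offer something in return. Enrollment order makes equal expected baselines plausible but does not guarantee them.

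Third, the SAP also wants within-group change, which a model of the follow-ups alone does not give. That is a reason to keep the ANOVA as a secondary analysis; it does not make the ANOVA the better arm comparison.

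A reader might go further and take the group main effect as the efficacy test. That term averages in a pre-treatment visit, estimates two thirds of a constant effect, and under the base assumptions has power of only 0.49, 0.41 and 0.35. But the SAP does not name it as the efficacy test, and the stated interest in change over time between groups points to the interaction. Those figures show why the term should be named; they are not a fault in what is planned.

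**Conclusion.** The point holds as one of efficiency. The group-by-time test in the SAP is a joint test of two change-from-baseline differences, and it is generally less precise than adjusting for baseline. Under equal SDs, a 0.8 SD effect and r of 0.3 to 0.7, the adjusted test gains 0.26, 0.17 and 0.07 in power. With a follow-up SD 1.5 times the baseline SD the gain is 0.08, 0.01 and −0.01. At r of about 0.9 it is close to zero, and for an effect of about 1.5 SD planned power is already 0.93 to 1.00.

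A reader might infer that the planned analysis is biased or invalid, or that it is bound to leave the trial underpowered. The documents support neither: the level is held, and they state no effect size, SD or correlation from which a shortfall could be shown. Nor is the loss tied to treating baseline as an outcome as such. It comes from leaving the arms' baseline means unconstrained. This is a cheap improvement, with moderate confidence.

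**What to change.** For FSQ, SPQ and BAT, the three scales for which the SAP lists a baseline value, take the between-arm result from a model of the one-week and one-month scores. Include group, visit, group by visit, the baseline score of that scale and baseline by visit, with an unstructured covariance. A longitudinal model with all three visits and a common baseline mean for the two arms is an equivalent option.

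Name the contrast in advance: either the 2-df joint test of the arm differences at the two visits, or the adjusted arm difference at one stated visit. The group-by-visit term will not serve, because in this model it asks only whether the effect differs between one week and one month, and it is null when the effect is constant.

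Adjust whatever the planned baseline comparison shows. Keep the three-timepoint ANOVA as a secondary analysis and for within-group change.

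The cost is some SAP text and one model per scale in software already listed, with no new data. Statistically, it spends one degree of freedom per visit, assumes linear and parallel baseline slopes, and assumes equal expected baselines under ABAB allocation; the SAP should state these assumptions.

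Timing also matters. The Protocol puts all sessions in 2019 and says "post hoc power analyses were conducted and are reported in the results section", while both documents are dated September 2020. Enter the change as a dated amendment and, if outcomes had already been seen, report both analyses side by side.
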